1.2 Hypotheses

1.2.1 Interfacing with primary care practices to encourage physicians to implement default online orders of blood glucose flowsheets and informational messaging for all patients with diabetes will increase patient adoption (as defined above).

1.2.2. Additional reminder messaging to patients that (1) emphasizes the value of tracking blood glucose data to the patient OR (2) emphasize the value of tracking blood glucose data to the doctor OR (3) informs patient of their selection for a chance to receive an award conditional on tracking will increase adoption relative to no reminder messaging.

1.2.3 Promotion of adoption of electronic blood glucose tracking through the means described above will result in the following intent-to-treat effects:

- (a) reduction in patient A1c
- (b) increases in frequency of doctor-patient interaction
- (c) changes to treatment plan path

1.2.4 Reminder messaging treatments that induce more intensive use of flowsheets will lead patients to experience larger effects as described in 1.2.3.

1.2.5 Entries of blood glucose data will be predictive of A1c on average and will lower over the study period.

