2.3 Duration of Study

Primary care practices identified in the treatment group will be encouraged to place bulk orders for electronic glucose flowsheets over a period of two weeks. Patients will be actively encouraged to use flowsheets for 12 weeks following the administration period. Outcome data will be collected for a total of 38 weeks:

- (a) 12 weeks retrospective at baseline
- (b) 2 week administration period
- (c) 12 week implementation period
- (d) 12 week follow up period

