3.1.1 PRACTICE LEVEL PROMOTION

Providers in the randomly selected group of treatment primary care practices will be encouraged to batch order blood glucose flowsheets for all patients with diabetes with active MyChart accounts. The research team will contact physicians and practice managers with an explanation of the initiative and instructions for completing batch orders and viewing entries through the system. The practice will be advised to complete filling orders over a two week administration period, after which the implementation period will begin. A batch order will trigger two forms of alerts sent to providers, according to the default settings for electronic glucose flowsheets:

1. A bi-weekly report received of values that the patient has entered, or a notification that the patient has not entered data during the interval.
2. A notification when patient entered values are out of range (the patient also gets a notification that their doctor will see this value) according to the following current settings:

Notification Setting	Current Default
Pre-Meal Range (entry outside range=alert)	60-180 mg/dl
Post-Meal Range	100-240 mg/dl
Nighttime Range	60-300 mg/dl

Patients will automatically be notified when the flowsheet has been ordered for them. Additionally, providers will be given text for a secure smart-text message to send to all patients receiving the flowsheets, instructing them to enter data for the study period. The secure message will also provide them with information on how to enter data, and on the benefits of tracking blood glucose. Draft text of this message is included below:

Dear [Patient],

You may have seen that there is a new electronic form available for you to enter your blood glucose results in the MyChart portal. Keeping track of your blood glucose can help you manage your diabetes and reduce your chances for developing complications like heart disease, kidney damage and eye damage. As part of a new Inova program to help patients with diabetes get healthy, I would like you to try entering the results of your home blood glucose tests on MyChart for the next 3 months, through [Date]. Please let me know if you have any questions.

Sincerely,

[Practitioner]

WHAT TO DO NEXT

1. **Get help:** If you need help learning how to measure your blood glucose or getting testing supplies, you can contact [Practice Contact].

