3.1.2 INDIVIDUAL LEVEL REMINDERS

After the initial two-week roll-out/administration period, follow-up emails will be sent out by the research team to patients at treatment practices whose doctors have placed blood glucose flowsheet orders. Patients will be assigned at the individual level to one of four reminder treatment conditions, which will be administered by the research team. The number of reminder conditions may be reduced (to 2 or 3 instead of 4) depending on the rate of flowsheet orders by physicians to preserve statistical power. Assignment to any of these treatments will not preclude or provide guidelines for other communication between providers and patients (e.g. providers are free to send out their own reminders or messaging regardless of patient assignment to treatment group). The four reminder treatment conditions are described below:

(1) No additional reminders from research group

(2) Standard secure message reminder, addressed from Inova Medical Group, sent every two weeks during 12 week implementation period. Draft text below:

*Dear [Patient],
Don't forget to track your blood glucose through MyChart! Keeping track of your blood glucose can help you manage your diabetes and reduce your chances for developing complications like heart disease, kidney damage and eye damage.
Sincerely,
Inova Medical Group*

(3) Secure message reminder with chance to receive gift card, addressed from Inova, sent every two weeks during 12 week implementation period. Draft text below:

*Dear [Patient],
You have been chosen for a special program to help you get started tracking your blood glucose through MyChart. For each day that you track your blood glucose on MyChart through [DATE], you will be*

entered to receive one of fifty \$50 gift cards to Amazon. You'll be sent a secure message through MyChart after [DATE] if you've been selected to receive a gift card. Keeping track of your blood glucose can help you manage your diabetes and reduce your chances for developing complications like heart disease, kidney damage and eye damage.

Sincerely,

Inova Medical Group

(4) Secure message reminder, addressed from primary care doctor, sent every two weeks during 12 week implementation period. Draft text below:

Dear [Patient],

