Outcome Measure: Intent to treat comparison of individuals between treatment and control practices of number of alterations to patient prescriptions/medication list during the intervention period and follow-up period

Hypothesis: Reminder messaging treatments that induce more intensive use of flowsheets will lead patients to experience larger effects as described above.

Outcome Measure: Intent to treat and treatment on the treated comparison of individuals across reminder messaging assignment groups (within treatment practices)-- reduction in A1c, increase in frequency of doctor-patient interactions, changes to treatment plan path (outcomes as described above in a-c)

Hypothesis: Entries of blood glucose data will be predictive of A1c and will lower over the study period.

Outcome Measure: Descriptive analysis of flowsheet entry values in the treatment group during the implementation and follow-up period.

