4.2 Method of Data Analysis

All data analyzed in this study will be administrative health and use data that is collected as part of routine medical care and record keeping. EPIC has offered to build the SQL queries required to produce the outcome datasets described in this protocol. Outcomes listed in Section 3.4. will be analyzed using regression analysis, including (a) a version with no covariates, (b) a version controlling for patient age/gender, race/ethnicity, A1c at baseline, days since most recent office visit at baseline, and doctor fixed effects. A flag identifying patients who are eventual participants of "Impact of Innovative Interventions on Diabetic Adherence with Digital Sensors" (a study recently submitted to the IRB that may have limited overlap with this population) will also be included in the controls. For outcomes indicating analysis of practice level treatment and control groups, standard errors will be clustered at the practice level.

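### Hypothesis 1.2.5 (flowsheet entries fall over the study) has no within-patient or meal-context measure, so a change in who enters, or when, can create or hide a trend

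*Combined protocol and SAP*

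**What the plan says.** Section 1.2 (1.2.5) states: "Entries of blood glucose data will be predictive of A1c on average and will lower over the study period". Section 3.4 repeats the claim and gives one measure for it: "Descriptive analysis of flowsheet entry values in the treatment group during the implementation and follow-up period". No unit of analysis, time contrast, comparator, weighting for number of entries, or rule for patients who stop entering is given.

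Section 4.2 adds a general rule: "Outcomes listed in Section 3.4. will be analyzed using regression analysis, including (a) a version with no covariates", and "b) a version controlling for patient age/gender, race/ethnicity, A1c at baseline, days since most recent office visit at baseline, and doctor fixed effects". The second version also carries a flag for participation in another study.

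Four design features bear on the point:

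- **Duration (2.3).** "Patients will be actively encouraged to use flowsheets for 12 weeks following the administration period"; a further 12 weeks of follow-up also count towards this measure.
- **Patient message (3.1.1).** It asks for at least 6 entries a week for 3 months, accepts occasional tracking, and sets no meal timing.
- **Alerts (3.1.1).** Default ranges differ by context: 60-180 mg/dl pre-meal, 100-240 for the row labelled "Post-Meal Range", and 60-300 at night. An out-of-range entry tells the patient that the doctor will see it.
- **Gift-card reminder (3.1.2).** "For each day that you track your blood glucose on MyChart through [DATE], you will be" entered for one of fifty gift cards, so in that arm the incentive depends on the number of days with an entry.

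**The concern.** The hypothesis is directional and concerns change over time, but the measure describes whatever values are entered. The set of people entering may well shrink and change, particularly once encouragement ends halfway through the window. If stopping is related to glucose level, the mean among those still entering moves although nobody's glucose has. The same happens if the share of post-meal readings drifts.

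At stake is a report that home glucose fell among flowsheet users, or that it did not, when the data show only a change in composition. The prediction half of the hypothesis is also open: if entries were pooled without a patient-level summary, frequent loggers would dominate. The plan does not say whether they would be pooled.

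**Working it through.** The plan gives no sample size, effect or error rate for 1.2.5, so there is no figure for this measure to reproduce. The only yardstick is the 0.27 detectable A1c effect in Section 4.1.

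**Yardstick.** There are 7,200 patients in 24 practices, so m = 300 per practice and 3,600 per arm, with ICC 0.07, SD 1.39 and baseline correlation 0.80. Two-sided 5% and 80% power are assumed.
- Design effect = 1 + 299 × 0.07 = 21.93; effective n per arm = 3,600 / 21.93 = 164.2.
- Detectable effect = (2.074 + 0.858) × 1.39 × √(2/164.2) × √(1 − 0.64) = 0.270. This matches the plan.

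**Step 1: selective stopping on the A1c scale.** If a share k keeps entering and stopping correlates ρ with glucose level, the mean of those remaining shifts by −ρ × SD × φ(z)/k, with z the normal quantile at 1 − k. The SD of 1.39 is from Section 4.1; k and ρ are assumptions.
- k = 0.5, ρ = 0.2: 0.2 × 1.39 × 0.798 = 0.22.
- k = 0.7, ρ = 0.1: 0.1 × 1.39 × 0.497 = 0.07.
- k = 0.3, ρ = 0.4: 0.4 × 1.39 × 1.159 = 0.64.

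The part of A1c not explained by baseline has SD 1.39 × √(1 − 0.64) = 0.83. If stopping depends on that part, baseline adjustment cannot remove the shift: at k = 0.5 and ρ = 0.2 it is 0.2 × 0.83 × 0.798 = 0.13.

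**Step 2: the same mechanism in mg/dl, over time.** Each patient's glucose is constant. Assumed: mean 150, between-patient SD 40, weekly probability of stopping 0.10 × HR^z, where z is glucose in SD units. The table gives the unadjusted mean among current loggers.

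| HR per SD | Weeks 1-4 | Weeks 9-12 | Weeks 21-24 |
|---|---|---|---|
| 1.0 | 150 | 150 | 150 |
| 1.25 | 149 | 141 | 131 |
| 1.5 | 147 | 134 | 120 |
| 0.8 | 151 | 159 | about 170 |

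The late columns rest on few people: with no link to glucose, 0.9^23 = 0.09 still enter in week 24, and with a link about 10% do.

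**Step 3: meal mix.** Taking the midpoints of the alert ranges as stand-ins gives (60 + 180)/2 = 120 pre-meal and (100 + 240)/2 = 170 post-meal. If the pre-meal share rises from 50% to 60%, 70% or 80%, the mean entry changes by 0.1, 0.2 or 0.3 × (120 − 170) = −5, −10 or −15 mg/dl.

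**Step 4: what the Section 4.2 models would leave.** The simulation has 720 enterers (3,600 × the 20% no-reminder adoption rate in 4.1), 24 weeks and 100 runs per setting, with no true change. Assumed: patient SD 30, reading SD 30, three entries a week, weekly log-odds of stopping −3 + s per SD of glucose, correlation 0.8 between baseline A1c and glucose level, and a 50 mg/dl pre/post gap from Step 3. Entries are the estimated 24-week change in mg/dl.

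| Scenario | No covariates | Baseline A1c only | Patient effects | Patient effects + meal |
|---|---|---|---|---|
| Stopping, s = 0.3 | −9.6 | −3.5 | 0.0 | 0.0 |
| Stopping, s = 0.6 | −16.2 | −6.2 | 0.2 | 0.1 |
| Pre-meal share 50% to 70% | −10.0 | −10.1 | −10.0 | 0.0 |
| s = 0.3 plus meal shift | −19.1 | −13.3 | −9.9 | 0.1 |
| Stopping reversed, s = −0.3 | +9.3 | +3.3 | −0.1 | 0.0 |

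Baseline A1c removes 1 − 3.5/9.6 = 64% and 1 − 6.2/16.2 = 62% of the drop-out artefact, and none of the meal-mix artefact.

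**The case against.** **The stakes are low, and the plan signals this.** 1.2.5 is the last of five hypotheses, its measure is labelled descriptive, and Section 4.1 names adoption and mean A1c as the key outcomes. Whether glycaemia improved is answered by the practice-randomised A1c comparison, which does not depend on who enters data. This stands and limits the point to 1.2.5. It does not remove it, because a directional hypothesis is stated and no caveat is attached.

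**The values are not simply raw.** A reader might infer that only unadjusted entries will be judged. The documents do not support that: read literally, Section 4.2 version (b) also adjusts for baseline A1c and doctor. The adjustment helps only in part.

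**The direction is not known.** A reader might infer that the measure will show a spurious fall. Nothing in the documents says which patients stop first or that meal timing will drift. If better-controlled patients stop first, the trend rises and a real fall could be hidden.

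**The sizes are assumed.** The documents give no drop-out rate and no glucose SD, and the alert ranges are notification settings, not measured distributions. This stands; the figures are illustrations. Nor do the documents say that gift-card entries are unreliable, or how entries will be combined to predict A1c, so neither can be claimed as a fault.

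**Conclusion.** The point holds for hypothesis 1.2.5 alone. A treatment-group description of entry values, with or without the Section 4.2 covariates, cannot separate change within patients from change in who enters or in when they test. The omission is plain from the text; its size and direction are not. Under the assumptions shown, the spurious 24-week change runs from about −19 to +9 mg/dl without covariates across the Step 4 scenarios. On the A1c scale the selection shift runs from 0.07 to 0.64, against the plan's 0.27 detectable effect. A within-patient, within-context trend stayed within 0.1 mg/dl of zero in the same scenarios, where stopping depends on a stable glucose level. It would not cure stopping that depends on a patient's own trajectory, regression to the mean, or secular trend, because entry values have no control comparison in this measure.

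A reader might go further and doubt the trial's adoption or A1c findings. The documents do not support that: those comparisons are between randomised practices and do not use entered glucose values.

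**What to change.** Reword the Section 3.4 measure for 1.2.5:

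1. Replace the pooled description with a within-patient trend, either patient fixed effects or paired early-versus-late windows, with equal weight per patient. Paired windows give equal weight directly; a model on individual entries needs weighting to do so.
2. Include meal context or time of day if it is recorded. The sponsor should confirm that the planned extract carries it, together with entry dates.
3. Report the number still entering over time, and the early values of those who stopped beside those who continued.
4. For prediction of A1c, use one summary per patient.
5. Label the result an uncontrolled trend, not an effect of the intervention.

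The cost is protocol wording and modest extra analysis of routine data, with no added patient contact. The downside is that fewer patients contribute to the trend, and those who do are the persistent loggers, so it describes them and not all who ever entered a value.

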3.5 Consent

A waiver of informed consent and waiver of HIPAA authorization is requested. The study is an encouragement design aiming to increase uptake of an existing service (electronic flowsheets) provided through Inova's MyChart electronic medical record system, and will not change standards of care. Patients and providers in both the treatment and control groups will have access to electronic flowsheets throughout the study unchanged from baseline. The research presents no more than minimal risk of harm to participants and involves no procedures for which written consent is normally required outside of the research context. Research could not practically be conducted without a waiver of consent and HIPAA authorization due to the number of subjects, online nature of the experiment, and design of the study which will seek to examine outcomes for the identified population regardless of actual use of electronic flowsheets. Outcomes of the research could not practically be studied without access to and use of protected health information. See sections on Data Storage, Risks and Confidentiality for more details.

3.6 Monitoring Subjects and Criteria for Withdrawal

Not applicable-- nature of encouragement design means that the intervention is discrete administration.

4. Statistical Considerations/Data Analysis

4.1 Sample Size

Non-pregnant adult patients of Inova primary care physicians with a current diabetes mellitus diagnosis and active MyChart account at time of treatment administration will be included in the study. The estimated number of patients is around 7200, from 71 primary care physicians across 24 selected Inova primary care practices.

Power Calculations

Power calculations were performed using the “clustersampsi” command in Stata. Knowledge of available sample and estimates/assumptions of control outcome mean, variance, and intraclass correlation were used to calculate a minimum detectable effect size for the key outcomes of flowsheet adoption (extensive margin, dichotomous rate of adoption) and changes in mean A1c.

Flowsheet Adoption: Practice Level Treatment-Control Comparison

Sample Size: 7200

Number of Treatment Arms: 2

Number of Clusters: 24

Assumed Control Adoption Rate: 2%

Assumed Intra-Cluster Correlation (within practices): 0.1

Minimum Detectable Effect: **9.5 percentage point increase in flowsheet orders**

Mean HbA1c: Practice Level Treatment Control Comparison

Sample Size: 7200

Number of Treatment Arms: 2

Number of Clusters: 24

Assumed Control HbA1c Mean: 6.74

Assumed Control HbA1c Standard Deviation: 1.39

Assumed Intra-Cluster Correlation (within practices): 0.07

Assumed Baseline Correlation: 0.80

ITT Minimum Detectable Effect: **0.27 change in A1c**

Flowsheet Adoption: Individual Level Comparison between Messaging Assignment Groups in Treatment Practices

Sample Size: 3600

Number of Arms (including no reminder): 4

Assumed No Reminder Adoption Rate: 20%

Minimum Detectable Effect: **5.5 percentage point increase in use of flowsheets when compared to no reminder**

Justification

The sample size represents the entire population of Inova primary care patients with diabetes who have active MyChart accounts and are therefore able to access the blood glucose tracking feature. The minimum detectable effects resulting from power calculations above are in-line with similar studies cited in the protocol background. Metastudy reviews of the effect of self monitoring of blood glucose found a 0.33 point change in A1c.

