3.3 Randomization

Provider-side treatments will be cluster randomized at the practice level. Randomization will stratify across practices by number of diabetic patients (cluster size), and will be conducted using a random number generator at the outset of the study. Reminder messaging treatments will be assigned alphabetically by first two letters of patient last name, as it is logistically infeasible to do individual level patient messaging without sorting on an existing field in the patient's EHR. There are some concerns that ethnicity could correlate with assignment based on last name spelling, so this form of assignment is "pseudo-random". However, the patient's race/ethnicity recorded in the medical record will be controlled for in the analysis. Causal interpretation of the results of the reminder messaging portion of the experiment will thus require the assumption that grouped last name spelling is not independently related to likelihood of flowsheet adoption.

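### The two practice-level minimum detectable effects (9.5 points; 0.27 A1c) match a calculation with equal-sized practices and are probably too small, because practice sizes are likely to differ and no allowance is listed

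*Combined protocol and SAP*

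**What the plan says.** Section 4.1 describes the sample thus: "The estimated number of patients is around 7200, from 71 primary care physicians across 24 selected Inova primary care practices". For both practice-level comparisons it lists "Number of Treatment Arms: 2" and "Number of Clusters: 24".

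- **Adoption:** "Assumed Control Adoption Rate: 2" per cent and "Assumed Intra-Cluster Correlation (within practices): 0.1". The resulting MDE is 9.5 percentage points.
- **A1c:** "Assumed Control HbA1c Standard Deviation: 1.39", an intra-cluster correlation of 0.07 and a baseline correlation of 0.80. The resulting MDE is "0.27 change in A1c".

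Neither list contains a practice-size range or CV. Alpha, sidedness and power are not stated either. The Justification paragraph says the MDEs are comparable with the cited studies and gives a 0.33 change in A1c from reviews.

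Section 3.3 says of the practices: "Randomization will stratify across practices by number of diabetic patients (cluster size". Section 3.4 defines the practice-level outcomes as comparisons of individuals. Section 4.2 specifies regression with standard errors clustered by practice and mentions no weighting of clusters.

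**The concern.** In a regression that gives every patient equal weight, large practices dominate the estimate. The variance therefore grows with the spread of practice sizes, even when the number of practices and the total sample are fixed. With a mean size of 300 and correlations of 0.07 to 0.1, almost all of the variance lies between practices, so the growth can be material. Stratifying by size balances the two arms' totals but does not remove this inflation.

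Two uses of the figures are at stake. Section 4.1 relies on the A1c MDE to argue that the trial can see effects of the published size. Section 1.1 makes the health analysis conditional on a statistically significant rise in adoption, so lost power on adoption also affects whether A1c is examined.

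**Working it through.** **Inputs from section 4.1.** 7200 patients and 24 practices in two arms: 12 practices and 3600 patients per arm, mean size m = 7200/24 = 300. ICC is 0.1 for adoption and 0.07 for A1c. Control adoption is 2%, A1c SD is 1.39, and baseline correlation is 0.80.

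**Assumed, because not stated.** Two-sided alpha 0.05; power 80%; t quantiles on 24 − 2 = 22 degrees of freedom, 2.074 + 0.858 = 2.932.

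**Step 1: reproduce the stated figures with equal practices.** Design effect DE = 1 + (m − 1) × ICC.

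- Adoption: DE = 1 + 299 × 0.1 = 30.9; effective n per arm = 3600/30.9 = 116.5. Solve d = 2.932 × √{[0.02 × 0.98 + (0.02 + d)(0.98 − d)]/116.5}. Result: d = 9.45 points (stated 9.5). The pooled-variance version gives 9.63.
- A1c: DE = 1 + 299 × 0.07 = 21.93; effective n per arm = 3600/21.93 = 164.2. SE = 1.39 × √(1 − 0.80²) × √(2/164.2) = 0.834 × 0.1104 = 0.0921. MDE = 2.932 × 0.0921 = 0.270 (stated 0.27).

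With equal sizes, normal quantiles give 8.9 to 9.0 points and 0.258. A power of 90% gives 10.9 points or more and 0.30 to 0.31. Neither matches.

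**Step 2: allow for unequal practices.** For equal patient weights, DE = 1 + [(1 + CV²) × m − 1] × ICC. Everything else is as in step 1. Power at 0.27 is from the noncentral t on 22 degrees of freedom with noncentrality 0.27/SE. The CV values are assumptions.

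| Assumed CV | DE, adoption | Adoption MDE (points) | DE, A1c | A1c MDE | Power at 0.27 |
|---|---|---|---|---|---|
| 0 | 30.9 | 9.45 | 21.9 | 0.270 | 80% |
| 0.2 | 32.1 | 9.71 | 22.8 | 0.275 | 79% |
| 0.3 | 33.6 | 10.03 | 23.8 | 0.281 | 77% |
| 0.5 | 38.4 | 11.05 | 27.2 | 0.300 | 71% |
| 0.6 | 41.7 | 11.72 | 29.5 | 0.313 | 68% |
| 0.8 | 50.1 | 13.39 | 35.4 | 0.343 | 60% |

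Example at CV 0.6, A1c: DE = 1 + (1.36 × 300 − 1) × 0.07 = 29.49; effective n = 122.1; SE = 0.834 × √(2/122.1) = 0.1067; MDE = 2.932 × 0.1067 = 0.313.

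**Step 3: find the thresholds.** At CV 0.1 the figures are 9.51 points and 0.271, which still round to those stated. The A1c MDE stops rounding to 0.27 at a CV of about 0.2. It reaches 0.33 at a CV of about 0.72.

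**Step 4: see what weighting would do.** If clusters were weighted efficiently (gamma-distributed sizes assumed), the MDEs would rise by about 0.4 to 0.6% at CV 0.5 and about 2% at CV 0.8. The equal-patient-weight rises are 11 to 12% from the square root of the DE ratio at CV 0.5, and 27% at CV 0.8. The adoption MDE rises further than that (13.39/9.45 = 1.42), because its variance also grows with d.

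**The case against.** The strongest objection is that the decisive input is unknown. No practice counts are given, and section 3.3 states no reason for stratifying and no spread. At CV 0.3 the A1c MDE moves only from 0.27 to 0.28, which is small beside the uncertainty in the assumed ICCs and in an approximate total of 7200. The losses at CV 0.8 rest on an assumption that no section supports. The penalty also depends on the estimator, since efficient weighting would recover most of it. This all stands. It limits the point to a direction and a range, and the table is close to a worst case for each CV.

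Three stronger readings are tempting and do not hold:

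- **That the figures arise only if every practice has exactly 300 patients.** A CV of 0.1 still rounds to both. Normal quantiles with a CV near 0.3 give 0.269 and 9.4 points. The input list omits alpha and power, so it is not a complete record. Equal sizes are the likeliest reading, not a proven one. The normal-quantile reading would not rescue the figures, however: with only 22 degrees of freedom, the same CV gives 10.0 points and 0.28.
- **That the design fails to deliver the stated MDEs.** That needs a CV the documents do not give. If practices are nearly equal in size, the figures are sound.
- **That the trial has no other power statement.** Section 4.1 also gives a 5.5-point MDE between messaging groups, which this point does not affect.

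That sizes vary is likewise an inference, but a fair one: stratifying on a quantity that hardly differs between practices would serve little purpose.

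**Conclusion.** The arithmetic in section 4.1 is not wrong; an allowance appears to be missing. Both practice-level MDEs match equal practices of 300, while section 3.3 implies unequal practices and section 4.2 plans no cluster weighting to offset that. The stated values are therefore probably optimistic.

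The size can be given only as a range. Over an assumed CV of 0.3 to 0.8, the A1c MDE is 4% to 27% above the reproduced 0.270, and the adoption MDE is 6% to 42% above 9.45 points. Below a CV of about 0.15 to 0.2 nothing of substance changes. The comparison with the 0.33 benchmark survives up to a CV of about 0.72, so a reader should not infer that it has already failed.

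The conclusion rests on two-sided 5%, 80% power, t quantiles on 22 degrees of freedom, equal patient weights and the ICCs in section 4.1.

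**What to change.** Rerun the two practice-level calculations with the practice counts that the stratified randomization requires. In section 4.1, restate both MDEs and show the CV of practice size, alpha, sidedness and power. Amend the Justification sentence that compares the MDEs with published effects if the restated A1c MDE no longer supports it. If a cluster-weighted analysis is intended, say so in section 4.2 and base the MDEs on it.

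The cost is one rerun and a text edit. Sample, arms and data collection stay as they are. The restated figures will probably be somewhat less favourable, and the messaging-group MDE needs no change on this account.

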2.1 Study Type

Cluster randomized encouragement design.

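### The 0.27 A1c minimum detectable effect is an all-patient ITT average, so section 4.1 does not compare like with like when it sets it beside a 0.33 effect of assigned self-monitoring

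*Combined protocol and SAP*

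**What the plan says.** Section 4.1 (Sample Size) computes an A1c MDE for 7200 patients in 24 practices, with SD 1.39, intra-cluster correlation 0.07 and baseline correlation 0.80. The result is 0.27, labelled ITT. The Justification that follows states: "The minimum detectable effects resulting from power calculations above are in-line with similar studies cited in the protocol background". The next sentence gives the only A1c benchmark: "Metastudy reviews of the effect of self monitoring of blood glucose found a 0.33 point change in A1c".

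The same section holds two adoption rates. The practice-level comparison uses "Assumed Control Adoption Rate: 2" percent and reports an MDE of a "9.5 percentage point increase in flowsheet orders". The comparison of reminder groups uses "Assumed No Reminder Adoption Rate: 20" percent with "Sample Size: 3600", which is half of 7200.

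Section 2.1 describes the trial as a "Cluster randomized encouragement design". Section 3.5 says outcomes are examined for the identified population "regardless of actual use of electronic flowsheets". Section 1.3 describes the background trials as ones that assigned patients to self-monitor, in one case six measurements a week. Section 1.1 makes the health analysis conditional on a significant rise in adoption.

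**The concern.** A reader who sees 0.27 beside 0.33 will conclude that the trial can detect the effect reported in the literature. If 0.33 were the true average over all patients in treatment practices, that would be right: power would be about 93% under the assumptions listed in the working.

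But the two figures answer different questions. Both may be ITT effects, but of different assignments. The cited trials assigned patients to test their glucose. This trial assigns practices to be encouraged to place orders, after which the patient may or may not enter data. The average effect over all patients is diluted by everyone whose behaviour does not change. No section multiplies the benchmark by an adoption difference, divides the MDE by one, or says why no conversion is needed. Section 3.4 mentions a treatment-on-the-treated comparison, but only across reminder groups and not for power.

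At stake is how an A1c result would be understood. The adoption condition in section 1.1 does not protect against this, because a significant rise in adoption is possible at contrasts far too small to yield 0.27.

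**Working it through.** **Inputs from section 4.1:** 7200 patients, 24 practices, SD 1.39, intra-cluster correlation 0.07, baseline correlation 0.80, adoption 2% (control) and 20% (no reminder).

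**Assumed, because the plan does not state them:** two-sided alpha 0.05, 80% power, 12 practices of 300 patients per arm.

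**1. Reproduce the plan's figure.**
- Design effect = 1 + 299 × 0.07 = 21.93.
- SE = 1.39 × √(1 − 0.80²) × √(2 × 21.93/3600) = 0.0921.
- MDE = (2.074 + 0.858) × 0.0921 = 0.270, using t quantiles on 22 df.

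This matches 0.27. The same assumptions, with intra-cluster correlation 0.1 (design effect 30.9) and 2% in control, give an adoption MDE of 9.4 points against the plan's 9.5. The assumptions are therefore probably those used.

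**2. Convert a per-adopter effect to an ITT effect.** If A1c changes only in patients induced to adopt:

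ITT effect = (treatment adoption − control adoption) × effect per induced adopter

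With 20% versus 2% the contrast is 18 points. Power is from the noncentral t on 22 df with SE 0.0921.

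| Effect per adopter | Source | ITT effect | Power |
|---|---|---|---|
| 0.33 | section 4.1 benchmark | 0.059 | 9% |
| 0.5 | adherent patients, section 1.3 | 0.090 | 15% |
| 0.69 | largest single-study value in the Cochrane review, section 1.3 | 0.124 | 25% |
| 0.9 | remote-monitoring system, section 1.3; type 1 patients, with added dose advice | 0.162 | 39% |

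**3. Invert the question.** An ITT effect of 0.27 at an 18-point contrast needs 0.27/0.18 = 1.5 A1c points per induced adopter. At 0.33 per adopter it needs 0.27/0.33 = 82 points of net adoption; at 0.5, 0.27/0.5 = 54 points.

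**4. Vary the contrast.**
- If all three reminder arms gain 5.5 points, the contrast is 18 + 0.75 × 5.5 = 22.1 points. The ITT effect is then 0.07 to 0.11 and power 12% to 21% for 0.33 to 0.5. The plan uses 5.5 points as an MDE, not a forecast.
- At 9.5 points the ITT effect is 0.03 to 0.05 and power 6% to 8%. The plan words that MDE as orders, so the contrast in patient use could be smaller.

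**5. Model without covariates.** Section 4.2 plans one version with no covariates and one with baseline A1c among its controls. Without baseline adjustment, SE = 1.39 × √(2 × 21.93/3600) = 0.153 and MDE = 0.45. Power at the 18-point contrast is 7% to 9% for 0.33 to 0.5. The 0.27 therefore applies only to an adjusted analysis. The doctor fixed effects in the adjusted version are not modelled here.

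**The case against.** The strongest reply has five parts.

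- **No number is wrong.** This is correct. A reader might infer that 0.27 is miscalculated. The documents do not support that, since it reproduces to three decimals. The fault lies in the sentence that interprets it.
- **The 20% is borrowed.** It belongs to the comparison of reminder groups and is not offered as a forecast for A1c. This stands, so every diluted figure is conditional. It does not clearly help the plan, though: under section 3.1.2 reminders go only to patients whose doctors have placed orders, and if 20% applies only to them the dilution is greater.
- **The benchmark already includes imperfect adherence, so the per-adopter effect may exceed 0.33.** This is fair, and is why 0.5, 0.69 and 0.9 are shown. Even at 0.9, from a different population with added dose advice, power at 18 points is 39%. The self-monitoring reviews and the 0.5 study concern patients not using insulin, whereas eligibility here is any diabetes diagnosis, so the right value is uncertain.
- **Effects may bypass flowsheet use.** Provider alerts (section 3.1.1) and hypotheses 1.2.3(b) and (c) envisage physician responses, and messages may prompt testing that is not recorded. This stands as a caveat. To reach 0.27 at an 18-point contrast with 0.33 per adopter, patients not induced to adopt would need a mean fall of (0.27 − 0.059)/0.82 = 0.26. The plan gives no such figure, and existing off-line monitoring would work the other way.
- **The sample is a census, so the comparison did not set its size.** True, and no larger sample is asked for. The claim of comparability is still made, and neither the census nor the ITT label makes it like for like.

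A reader might also infer that the plan will treat a non-significant A1c result as showing that self-monitoring does not work. No section says so. Section 1.1 promises to consider why health indicators do or do not improve.

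**Conclusion.** The point holds as one of interpretation, not arithmetic. Section 4.1's 0.27 is sound under the assumed alpha, power and allocation and with baseline correlation 0.80. It is not comparable with 0.33 without a conversion for partial adoption, and the plan offers none.

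If adoption is 20% versus 2% and effects run only through induced adoption, 0.33 to 0.5 per adopter becomes an ITT effect roughly a fifth to a third of the MDE (0.059/0.27 = 0.22; 0.090/0.27 = 0.33), and power falls far below 80%. The direction survives every per-adopter value and adoption contrast tabulated above.

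It would go too far to state as fact that the trial has 9% to 15% power for A1c. Those figures rest on a borrowed adoption rate, an adoption-only pathway and design parameters the plan leaves unstated. What the documents do support is that the stated justification claims a sensitivity to the literature effect that the plan has not shown.

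**What to change.** For A1c, replace the sentence in section 4.1 that claims comparability with:

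> The 0.27 MDE (baseline-adjusted; [alpha, power and practices per arm, to be confirmed by the sponsor]) is an average effect over all patients in encouraged practices and is not directly comparable with the 0.33 from trials that assigned self-monitoring. If adoption is 20% vs 2% and A1c changes only in patients induced to adopt, 0.33 to 0.5 per adopter implies an ITT effect of about 0.06 to 0.09 and power of about 9% to 15%. Effects through physicians or unrecorded testing would raise these figures; existing off-line monitoring would lower them.

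Recompute the ranges if the confirmed values differ from those assumed here. A sentence in section 4.2 saying that A1c results will be given with confidence intervals, and that a non-significant result will not be read as evidence of no effect, would be useful but is optional.

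The cost is a less favourable stated case for A1c. No patients are added and the planned analysis does not change.
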